The purpose of this study is to further develop the techniques to permit the imaging of infant lungs with hyperpolarized helium-3 MRI including techniques for acquisition in free breathing infants and infants on a ventilator. We have developed fast imaging techniques and obtained proof-of-concept data in infants as young as 2 months old. Many pediatric lung diseases including CF, bronchopulmonary dysplasia (BPD) and asthma have their origins in infancy so it would be desirable to be able to image infants with hyperpolarized gas MRI. We focused on developing fast imaging techniques to, in essence, freeze lung motion in non-sedated infants. We feel the technique will be more widely adopted if clinically useful images can be obtained without sedating the infant. Some very rapid imaging techniques have been developed for conventional proton MRI for applications such as cardiac MRI that require very short acquisition time. We modified these techniques for use in hyperpolarized gas MRI and developed a technique that permits the acquisition of the entire lung volume of an infant in less than 1 second. These techniques would also be useful for imaging infants who are still on a ventilator with the hope of increasing our understanding of lung development and neonatal lung disease. This is a technical development and proof-of-concept study. From our prior experience developing new techniques for hyperpolarized gas MRI, we anticipate 60 subjects will be required for the sequence development portion of the study. An additional 30 subjects [10 healthy, 10 with CF, and 10 bronchopulmonary dysplasia (BPD)] will be imaged as part of the proof of concept study. As a Phase I pilot technology development and proof of concept study, no formal statistical analyses are planned.

NOTE: Infants (under one year of age) who are ventilator dependent will not be enrolled until more data is available on non-ventilator dependent infants (under one year of age). The infant data must be reviewed and approved by the IRB-HSR before ventilator dependent infants may be enrolled.

Background

1. Provide the scientific background, rationale and relevance of this project.

Development of Rapid Imaging Techniques for use in Infants: Today, there is a fundamental requirement for a safe, non-invasive method for assessing the character and severity of childhood obstructive lung diseases in early development. To meet this unmet need, we are developing rapid helium MRI of the lung in non-sedated infants and children. This innovation will make it possible for the first time to provide important insights for the clinical management of pediatric lung disease in this population at risk. In this regard, we propose to deploy our approach for measurement of lung function in healthy children, cystic fibrosis (CF) (a progressive disease that substantially alters lung function with substantially reduced life expectancy), and BPD (chronic lung disease of prematurity). While it is possible to identify babies with these diseases, there are essentially no tools available to evaluate the efficacy of therapies that may prevent irreversible damage to the lungs. This study will enable imaging of lung function at the earliest stages of lung disease to allow intervention at the earliest stages of disease.

Despite widespread newborn screening and significant improvements in the management of CF, the severity of the associated pulmonary disease increases with age, culminating in life-threatening complications. Fortunately, in recent years several promising new therapies have emerged. However, the greatest impediment to the clinically meaningful evaluation of treatment outcomes remains the lack of an adequate measure of lung function in neonates and young children.

With the advent of surfactant therapy, prenatal steroid treatment of mothers in premature labor, and changes in ventilator support of premature infants, the mortality from lung disease has substantially decreased but the incidence did not decrease. The current thought is that the development of the lung in premature infants is altered resulting in a disruption of alveolar development. Early intervention with a treatment that would improve alveolar development could greatly improve the lives of these children. Our hope is that if our technical development is successful, hyperpolarized helium-3 could be used as an outcome measure in clinical trials of such treatments.

Hyperpolarized Helium-3 MRI: Hyperpolarized helium-3 (3He) gas magnetic resonance (MR) imaging is a relatively new technique for evaluating the lungs. With this test the lung airspaces are directly visualized by inhaling the hyperpolarized gas. Preliminary studies have shown the potential of visualizing the small airways after inhalation of relatively small quantities of gas, allowing assessment of ventilation abnormalities (3-5). More recent developments including our own have shown that with this technique, an indirect measurement of the lung airspaces, may be obtained by measuring the diffusion of the helium-3 gas in the lungs (6). Preliminary studies have shown that hyperpolarized helium lung MR can potentially be used to assess diffuse lung diseases such COPD (7-10), asthma (11), cystic fibrosis (12). However, the full extent of this technique in evaluating these diseases is yet to be established.

Hyperpolarization of the Helium 3 gas:

1. Original polarizer:

- The method for polarizing the helium-3 gas uses the technique of spin-exchange optical pumping. The polarization process is performed in a glass cell filled with helium-3 gas and a few milligrams of alkali metal (rubidium).
- The glass cell is heated to vaporize the alkali metal, and the cell is then illuminated for approximately 10-12 hours with circularly polarized laser light, allowing the helium-3 to become polarized through a process called spin exchange.
- The alkali metal is needed to facilitate the transfer of spin from the laser light to the helium-3 atoms.
- After polarization is complete, the cell is cooled down to allow the alkali metal to return to the solid state, and it condenses on the inside of the glass cell.
- The polarized helium-3 gas is then released from the cell and passes through a 20-micron adsorption filter that removes any residual alkali-metal vapor.
- The filtered gas is dispensed into a bag and inhaled by the study subject through the mouth for imaging of the lungs, or through the nose for imaging the sinuses using H3He MRI.

2. Second helium polarizer: Built under the direction of [name] in the physics department and [name] in radiology, it generates larger batch volumes with higher net polarization than our original helium polarizer.

- The operating principles of the new polarizer are identical to those of the original polarizer. In both systems, helium polarization is carried out in a heated glass cell filled with helium gas and a few milligrams of alkali metal (rubidium and/or potassium). After polarization is complete, the cell is cooled down to allow the alkali metal to return to the solid state. The polarized helium gas is then released from the cell, mixed with medical-grade nitrogen, and dispensed into a dosing bag for inhalation by the subject. All tubing and valves used for handling and dispensing the helium gas were manufactured according to oxygen-clean standards, which is the most stringent cleaning specification for gas-handling systems.

- The only functional difference between the two polarizers is that rubidium is the only alkali metal used in the original polarizer, whereas a mixture of rubidium and potassium is used in the new polarizer. The safety procedures used in the original polarizer, which ensure that none of the alkali metal in the cell escapes into the dispensed helium, are duplicated in the new polarizer:
 - The cell temperature is monitored continuously during the cooling process, and we wait until the cell temperature has been below 40°C (104°F) for at least 30 minutes before dispensing the polarized helium. This ensures that there is enough time for the rubidium and potassium vapor to condense out of the gas phase.
 - The polarized helium is released from the main body of the cell through a capillary stem that precedes the cell valve. The capillary stem provides additional surface area for any residual alkali vapor to condense onto, and ensures that virtually all of the rubidium and potassium remains behind in the glass cell.
 - For good measure, the dispensed helium passes through a 20-micron filter at the outlet port. This filter would remove any solid alkali metal if it happened to escape from the cell, although tests of unfiltered gas show that this step is probably not necessary.
- To verify the effectiveness of these safety measures, helium was polarized according to standard operating procedures, and a standard human dose was dispensed into a gas-sampling bag. This bag was sent to an independent laboratory (Element One, Wilmington, NC) for analysis. The gas sample and the inside surface of the bag were both tested for the presence of rubidium, potassium, and silicon, using exactly the same type of analysis (ICP-MS) that was performed on gas from our original polarizer. No traces of these elements were found at the machine detection limits.

3. Third method for Helium Polarization: As interest in hyperpolarized gas imaging has increased, there is a need to develop a method for providing polarized helium gas to sites that are not equipped with an onsite polarizer.

- With this third method, the polarization of the helium gas will occur in a polarization device at our industry partner, Xemed, LLC in New Hampshire. As with the two methods described above, helium polarization is carried out in a heated glass cell filled with helium gas and a few milligrams of alkali metal (rubidium and/or potassium). After polarization is complete, the cell is cooled down to allow the alkali metal to return to the solid state. The polarized helium gas is then transferred to a glass cell for transport to the site. At the site the polarized helium gas will be dispensed from the glass cell into teflon (a type of plastic) bag. It may be mixed with medical-grade nitrogen to achieve the appropriate volume for inhalation by the subject. All tubing and valves used for handling and dispensing the helium gas are manufactured according to oxygen-clean standards, which is the most stringent cleaning specification for gas-handling system. As above, the gas from this method was sent for purity testing and no traces of other elements were found at the machine detection limits. A purity report of the dispensed helium gas is attached.
- The gas transportation system: The helium gas is polarized offsite at Xemed. Then, it is pumped into a 1 L iron-free glass transport cell and placed in a metal container with a permanent shielded

(0.8 mT) magnet to protect against stray external magnetic fields (pictured below). The filling pressure of the gas allows 1 L of useable gas when released. The container is then shipped to the imaging center where it is transferred to the tedlar bags and administered to the subject. This system has been previously tested successfully in Europe and Australia. (21, 22)

Hypothesis to be Tested

The purpose of this study is to further develop the technique of rapid hyperpolarized helium-3 MRI for use in infants, and perform a pilot study in infants who are healthy and infants with CF, BPD, and asthma.

Study Design: Biomedical

1. Will controls be used? No.

2. What is the study design?

Pilot.

3. Does the study involve a placebo?

No.

Human Participants

Ages: 1 month -65 years old

Sex: Both

Race: All

Subjects- see below

- 1. Provide target # of subjects (at all sites) needed to complete protocol.** 110.
- 2. Describe expected rate of screen failure/ dropouts/withdrawals from all sites.** 10%.

- 3. How many subjects will be enrolled at all sites?** 121.
4. How many subjects will sign a consent form under this UVa protocol? 121.
- 5. Provide an estimated time line for the study.** We expect to complete this study in 5 years.

Inclusion/Exclusion Criteria

1. List the criteria for inclusion

We confirm that this protocol includes two arms: 1) one that enrolls adults and children age >1 month to fine tune the details of the MRI sequence acquisitions and 2) a pilot study that enrolls infants and young children age >1 month with either healthy or diseased lungs. Some of the subjects in arm 2 may be on a ventilator and ready to wean.

MRI sequence development (n=60):

Healthy subjects and patients with CF, BPD, asthma, COPD, a history of smoking or other lung diseases will be used in the development of the rapid imaging techniques. These subjects will be age 1 months to 65 years old. Healthy subjects can have no history of chronic respiratory disease. The subjects with CF, asthma, or BPD must have a physician diagnosis of their respective disease.

Pilot Study (n=50):

Twenty healthy infants, 10 infants with CF, and 20 infants with BPD age 1-24 months will be imaged in the proof-of-concept study. Healthy infant must have had an uncomplicated term birth and have no history of chronic respiratory symptoms. Infants with BPD must have a physician diagnosis of BPD. The patients with CF must have a physician diagnosis of CF and be at their baseline clinical status on the day of imaging. In order to enroll infants with normal lungs who are being ventilated, we will include infants with a perinatal hypoxic ischemic event (HIE) as healthy subjects.

Some subjects may be invited to return for an additional MR imaging visit and the subsequent follow up (as described below) after approximately 5 months from their first visit. Before this is done, the participant will sign the consent form again.

If a child is on a ventilator, they must either meet the criteria for being ready to be weaned from the ventilator or clinically stable on a home ventilator. An MRI compatible ventilator will be used while the patient is in the scanner.

2. List the criteria for exclusion

- Any condition for which a MRI procedure is contraindicated.
- Presence of any non-MRI compatible metallic material in the body, such as pacemakers, metallic clips, etc.
- Likelihood of claustrophobia.
- Chest circumference greater than that of the helium MR coil.
- Pregnancy, by report of subject. Clinically in the Department of radiology at UVA, self-report is used when screening patients for MR scans as well as CT scans and fluoroscopy studies. If the subject

reports there is any chance of their being pregnant, a urine pregnancy test will be performed prior to any imaging.

3. List any restrictions on use of other drugs or treatments.

Inhaled medications such as short acting beta-2 agonists should not be administered within 4 hours prior to the hyperpolarized helium-3-MRI.

Statistical Considerations

1. Is stratification/randomization involved? No.

2. What are the statistical considerations for the protocol?

The goals of this project are to further develop the technique of hyperpolarized helium-3 MRI for use in infants and to perform a small pilot study in 30 infants to demonstrate the technique could be expanded to a larger clinical trial. No formal statistical analyses are planned. For the images obtained as part of the proof-of-concept study, we will measure conventional metrics of image quality such as signal-to-noise ratio (SNR) to quantify the image quality obtained with our technique. However, no comparison with our historical data in cooperative, older subjects is planned. In addition, we will calculate as a measure of disease severity, the percent of the lung volume that is poorly ventilated.

3. Provide a justification for the sample size used in this protocol.

The sample size for the MRI sequence development portion of this study is derived from our long experience in developing new techniques for hyperpolarized gas MRI. Best guess estimates are initially used for the sequence parameters but the sequences must be tested and refined in human subjects because the complex interactions of the lung microstructure, the hyperpolarized gas signal characteristics, and sequence parameters are difficult to predict, so much trial and error is used in the development. The sample size for the proof-of-concept trial is the smallest number to demonstrate that the technique is both feasible and robust in both healthy infants and infants with lung disease.

4. What is your plan for primary variable analysis?

No formal statistical analyses will be required, and none are planned.

5. What is your plan for secondary variable analysis?

We will compare the measures of image quality and disease severity between the 10 healthy infants, the 10 infants with CF, and the 10 infants with BPD. However, we do not expect there to be significant differences between these two groups with this low number of subjects.

6. Have you been working with a statistician in designing this protocol? No.

7. Will data from multiple sites be combined during analysis? No.

Biomedical Research

1. What will be done in this protocol?

All study procedures, including MR imaging, will take place at the Snyder Building at Fontaine Research Park or the main radiology department in the hospital.

- A medical history will be taken defining any present and past history of respiratory illnesses, medications, and hospitalizations and the ability to have MR imaging.
- A urine pregnancy test will be done for women of childbearing potential, who report the possibility that they might be pregnant.
- If needed, a practice bag filled with room air will be given to the subject as a teaching tool to teach the subjects the breathing technique used during the administration of hyperpolarized helium gas.
- Before and after MR imaging, a physical exam, spirometry (if subject able to perform test), and a baseline %PO₂ will be performed.
- During the MR imaging procedure, the subject's heart rate and blood oxygen saturation will be monitored using an MR compatible pulse oximeter when possible.
- Once positioned in the MR scanner, the free breathing MR imaging will be performed.
- Then, the hyperpolarized helium 3 imaging will be performed.
 - Subjects who are infants will be bundled or held to restrain motion while in the MRI scanner
 - Infants will be placed in the MR coil such that their head is supported in a neutral position. Imaging occurs very quickly so the total time the subject is expected to be in the scanner is less than 15 minutes.
 - For infants with BPD, a physician from the research team will be present at all imaging sessions to monitor the subject. Imaging will be terminated if the physician feels the baby is being unusually stressed in any way.
 - Imaging will be terminated and oxygen given if the subject's pO₂ on pulse oximetry drops by 10% or more or if there is a sustained low heart rate over one minute of less than 100 bpm heart rate. We have experience with MR imaging of young infants for clinical brain MRI and most infants tolerate imaging of the brain MRI well. We expect infants to tolerate the lung imaging well particularly since the duration of imaging will be less than brain MRI.
 - If the subject is not on a ventilator, the subject will inhale the hyperpolarized gas which may be mixed with medical grade nitrogen through a small plastic tube connected to a plastic bag containing the hyperpolarized gas mixture or through a face mask or other gas delivery device. If the subject is on a ventilator the hyperpolarized gas mixture will be introduced into the ventilator circuit just before the endotracheal or tracheostomy tube.
 - Rapid MR imaging will be performed during inhalation/exhalation and/or breath-hold. Depending upon the availability of gas and the quality of images obtained, the helium-3 inhalation and MR imaging may be repeated.
 - Oxygen by nasal cannula or mask may be administered immediately before and after gas inhalation.
 - The dedicated transmit/receive MR coils used for the gas imaging is an investigational, non-FDA approved device. However, the manufacturer considers it a non-significant risk device. In addition, non-standard MR pulse sequences are used for hyperpolarized gas imaging. In general these sequences require much lower power depositions than conventional MR imaging and therefore include no significant risk.

- Conventional proton images of the thorax may also be obtained to define the lung boundaries for subsequent image analysis.
- May use an inline flow meter to measure the airway flow and gas volumes during dosing with practice bags outside of the scanner and with dosing bags while in the scanner.
- The total time of the MR image acquisition is limited typically less than 20 seconds. The total study visit duration is expected to be 3-4 hours.

Subjects will be contacted from 1-5 days via telephone or email after imaging to assess for side effects and adverse events.

NOTE: Gadolinium will not be used for this study.

2. List the procedures, in bullet form, that will be done for RESEARCH PURPOSES as stipulated in this protocol.

All procedures are being done for the research study.

3. Do you confirm that, except for blood draws through a peripheral site, that all invasive procedures will be performed by a licensed health care provider under the supervision of an MD? Yes.

4. Will you be using data/specimens in this study that were collected previously, with the use of a research consent form, from another research study? No.

5. Will any of the procedures listed in item # 2 have the potential to identify an incidental finding? This includes ALL procedures, assessments and evaluations that are being done for RESEARCH PURPOSES that may or may not be considered investigational. Yes.

► IF YES, check one of the following two options:

The examination(s) utilize(s) the same techniques, equipment, etc., that would be used if the subject were to have the examination(s) performed for clinical care. **There exists the potential for the discovery of clinically significant incidental findings.** (limited physical exam, spirometry, urine pregnancy test, if needed, vital signs)

- The PI takes full responsibility for the identification of incidental findings:
- The PI will inform the subjects verbally of all incidental findings that are of clinical significance or are of questionable significance.
- A follow-up letter describing the finding should be provided to the subject with instructions to either show the letter to their PC or if the subject has no PCP, the subject should be instructed to make an appointment at UVa or at the Free Clinic.

This examination(s) utilizes non-standard/investigational, technique, equipment, etc. It is impossible to determine the significance of such results, therefore abnormalities will not be shared with the subject because the meaning of the exam is not yet proven and is of unknown clinical benefit. (Helium MRI)

6. Do any of the procedures listed above, under question # 2, utilize any imaging procedures for RESEARCH PURPOSES? Yes.

IF YES, list procedures:

MRI with helium.

This imaging research examination utilizes non-standard/investigational imaging modality, techniques, equipment, scanning sequences, etc. It is impossible to determine the significance of such images, therefore abnormalities will not be shared with the subject because the meaning of the exam is not yet proven and is of unknown clinical benefit.

7. Will you be using viable embryos? No.

8. Will you be using embryonic stem cells? No.

9 Are any aspects of the study kept secret from the participants? No.

10. Is any deception used in the study? No.

11. If this protocol involves study treatment, explain how a subject will be transitioned from study treatment when they have completed their participation in the study.

NA, study does not involve a treatment.

12. Will your study involve measures (C-SSRS/BID/SCID etc.) used to assess for depression and/or suicidality for research purposes? No.

13. Where will the study procedures be done?

Check One:

UVA medical center facilities (In patient or outpatient)
 UVa , but not medical center facilities: LIST specific location Snyder Building

14. If the study involves medical risk and study procedures will be done outside of the UVa Medical Center what is your plan to protect the subjects in case of a medical emergency?

Study coordinator onsite during procedures
 Individual trained in CPR on site during procedures
 AED and Individual trained to use it onsite
 Call 911

Specimens

Specimen Information

1. Describe the type of specimen to be used: urine

2. Will the specimen be obtained BEFORE a subject has signed a consent form? No

3. Will you be using discarded specimens? No

Specimen Labeling

1. What information/ HIPAA identifiers will be on the specimen label when it is given to the study team (from clinical labs or other source outside the study team) and/or what information will you put on the specimen?

none, specimen will be processed at point of care

2. If the specimen is given to the study team with information on the label will you delete any of the information on the specimen label?

Not applicable

3. Will any additional data be linked to the specimen by way of a code? No

4. Will the analysis on the specimen be done soon (within 24 hours) after it is collected? Yes

Specimen Shipping

1. Do you plan to ship any specimens outside of UVA? No

Data and Safety Monitoring Plan

1. Definition:

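### The pilot is sized to show feasibility, but every planned measure needs an obtained image, so no planned analysis counts infants who yield none; the pilot size is also given as both 30 and 50

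*Combined protocol and SAP*

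**What the plan says.** **Aim.** Statistical Considerations, item 2, gives one goal as "to perform a small pilot study in 30 infants to demonstrate the technique could be expanded to a larger clinical trial". Item 3 says the proof-of-concept number "is the smallest number to demonstrate that the technique is both feasible and robust in both healthy infants and infants with lung disease".

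**Measures.** Item 2 continues: "For the images obtained as part of the proof-of-concept study, we will measure conventional metrics of image quality such as signal-to-noise ratio (SNR"). It adds the percentage of lung volume that is poorly ventilated, as a measure of severity. Item 4 plans no formal primary analysis. Item 5 compares image quality and severity "between the 10 healthy infants, the 10 infants with CF, and the 10 infants with BPD", and says that significant differences are not expected.

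**Conduct.** Biomedical Research, item 1, allows imaging to be stopped on the physician's judgement of stress (stated for infants with BPD) or on saturation or heart-rate criteria (any subject). It also lets inhalation and imaging be repeated, depending partly on image quality. The Pharmacy appendix, item 3, allows up to 10 doses per session. Payment, item 2c, provides for a visit that cannot be finished. The inclusion criteria add that "Some subjects may be invited to return for an additional MR imaging visit", about five months after the first.

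**Pilot size.** The opening summary says "An additional 30 subjects [10 healthy, 10 with CF, and 10 bronchopulmonary dysplasia (BPD)] will be imaged". The inclusion criteria say "Pilot Study (n=50") and "Twenty healthy infants, 10 infants with CF, and 20 infants with BPD age 1-24 months will be imaged in the proof-of-concept study".

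**The concern.** A claim that a technique is feasible in unsedated infants is a claim about a proportion: of the infants attempted, how many gave an image that could be used. The plan has no numerator, denominator or criterion for it. SNR on the images that exist describes how good the successes are and says nothing about how often success occurs. A poor image still shows up as low SNR, but an absent image leaves no trace in the planned results. Anyone sizing the larger trial that the pilot is meant to support would need the missing proportion.

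Item 5 has a related gap. An infant may have several acquisitions in one session and a second visit later, and no rule says which of them represents the infant in the group comparison. The infants missing from each group would not be shown either.

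The two pilot sizes matter here because they fix the denominator, and so the precision, of any feasibility statement.

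**Working it through.** **1. Does any planned measure survive without an image?**

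| Planned quantity | Statistical Considerations | Needs an image? |
|---|---|---|
| SNR and similar quality metrics | item 2 | yes, by its own wording |
| Percentage of lung poorly ventilated | item 2 | yes, calculated from the image |
| Primary analysis | item 4 | none planned |
| Group comparison | item 5 | yes, same measures |

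**2. Are infants without an image counted elsewhere?** Withdrawals and dropouts go to the IRB on the continuation form (Data and Safety Monitoring Plan, 2.6). The investigator's annual review lists early withdrawals (5.3). Adverse events are recorded whether or not an image exists (3.1). None of these defines a scanned infant without a usable image, and none supplies a count of infants attempted. Human Participants allows 121 − 110 = 11 non-completers, but that figure pools screen failures, dropouts and withdrawals over both arms.

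**3. The plan's own total, and the two pilot sizes.**
- Inclusion criteria: 20 + 10 + 20 = 50, and 60 + 50 = 110. Then 110 × 1.10 = 121, which reproduces the stated enrolment.
- Opening summary and item 5: 10 + 10 + 10 = 30, and 60 + 30 = 90. Then 90 × 1.10 = 99, which does not.

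The enrolment total therefore follows the 50, while Statistical Considerations still works from 30.

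**4. What the planned results could not distinguish.** The inclusion criteria give group sizes as infants who are imaged. Suppose recruitment continues until the target is imaged, with an assumed success rate p (the documents give none). Infants attempted = target / p, rounded up:

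| Assumed p | Attempts for 30 imaged | Attempts for 50 imaged |
|---|---|---|
| 100% | 30 | 50 |
| 90% | 34 | 56 |
| 80% | 38 | 63 |
| 70% | 43 | 72 |
| 50% | 60 | 100 |

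The planned measures would have the same number of infants behind them in every row of a column. This illustrates the gap and does not estimate it.

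**5. Precision at the two pilot sizes.** With n successes in n infants, the exact (Clopper–Pearson) two-sided 95% lower bound is 0.025^(1/n).

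| n | Lower bound, no failures | 95% interval, one failure (illustration) |
|---|---|---|
| 10 | 69.2% | 9/10: 55.5–99.7% |
| 20 | 83.2% | 19/20: 75.1–99.9% |
| 30 | 88.4% | 29/30: 82.8–99.9% |
| 50 | 92.9% | 49/50: 89.4–99.9% |

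With no failures, the choice between 30 and 50 moves the overall bound by 92.9 − 88.4 = 4.5 points. The choice between 10 and 20 moves the healthy and BPD bounds by 83.2 − 69.2 = 14.0 points. CF is 10 in both versions, so its bound stays at 69.2%.

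**The case against.** The strongest reply is that this is a declared technology-development pilot with no formal statistics. Feasibility appears in the sample-size justification and not as an endpoint, and nothing forbids the investigators from saying how many infants were imaged. That is fair as far as it goes, and it is why a descriptive count is enough. But the justification names a conclusion, and the listed measures cannot deliver it.

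Several stronger readings are tempting and do not hold:

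- *Infants without an image disappear altogether.* The administrative routes in step 2 may record some of them. The gap is in the planned analysis.
- *Every stopped or unfinished session is a failure.* The opening summary puts whole-lung acquisition at under 1 second, and Biomedical Research puts total acquisition typically under 20 seconds. A session can be stopped with a usable image already taken. The payment clause covers any reason and both arms.
- *Image loss differs between groups.* The stress provision is stated for infants with BPD, which might suggest this. The documents do not show it, and Biomedical Research expects infants to tolerate imaging well.
- *The 4.5 and 14.0 points measure the harm from the missing denominator.* They measure only the conflict in pilot size.
- *The 11 non-completers estimate imaging failures.* They cannot, because they include screen failures and both arms.

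On item 5, the plan never says that each infant contributes one value, and the comparison is descriptive. The result can still change with the acquisition chosen, so the choice should be written down. No decision depends on it.

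**Conclusion.** The point stands in limited form. Followed as written, the plan describes the images obtained and gives no proportion of infants in whom the technique yields a usable one, which is what its own stated conclusion needs. The size of the effect is unknown because the documents contain no failure rate, and no bias between groups is shown. Without a count of infants lacking an image in each group, a reader could not check for one.

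The pilot-size conflict is a separate and plain contradiction in current text. Its consequence is precision only, as in step 5, and those bounds assume no failures.

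The change is worth making before pilot images are assessed. It does not bear on safety or eligibility.

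**What to change.** 1. **Statistical Considerations, items 2 and 4.** Make the main descriptive result the number and proportion of infants brought to the scanner at the first visit who yield an analysable helium image, overall and by group, with exact 95% intervals. Write the criterion for an analysable image before any pilot image is assessed. Keep every such infant in the denominator and list the reason for each failure. Show gas-supply failures as their own category, and give a second proportion that excludes them.
2. **Item 5.** Name in advance one acquisition per infant, for example the first analysable image from the first visit. Keep second visits separate, and show the number without an image in each group beside the comparison.
3. **Pilot size.** Reconcile 30 (10/10/10) with 50 (20/10/20) in the opening summary, the inclusion criteria and Statistical Considerations items 2 and 5, and check the enrolment total against the result.

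No hypothesis test and no change to dosing or clinical conduct is involved. The cost is a few sentences, one written criterion and a short log for each infant brought to the scanner. The downside is that group intervals will be wide and the headline may look less favourable than SNR on obtained images alone.
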